The effect of progressive balance exercise on postural sway – a 4 week randomized controlled trial

Today most fracture prevention measures targets the bone and osteoporosis. However, only about 20% of individuals with fractures have osteoporosis and at least 90% of all fractures are caused by a fall. Therefore, the present project builds on previous findings from our group identifying postural sway as an important risk factor for falls and aims to intervene against this risk factor in a randomized controlled trial targeting subjects at the highest risk for falls.

Specific aims:

1. Examine whether four weeks progressive balance training can improve parameters of body sway in measurements of static standing balance
2. Investigate whether participants experience greater security to their own ability and less fear of future falls after 4 weeks of progressive balance training
3. Investigate how long a potential effect of progressive balance training may be noticeable on participants' experiences of greater security in their own ability and less fear of future falls
4. 3. Examine whether participation in balance training leads to reduced number of falls at follow-up after 6, 12 and 24 months

Background

Falls and fall-related injuries are major health concerns for elderly individuals; they cause functional decline and increased mortality, as well as incurring vast health care costs for society.¹⁻³ Occurrences and consequences of falls are expected to increase globally with the growing number of elderly individuals. Hence, the improved detection and prediction of potential fall risk markers are of individual and societal importance.

Falling can be the end result of intrinsic and extrinsic factors negatively affecting an individual's ability to maintain balance,⁴ which are often revealed during sequences of body movement.⁵ Balance can be both dynamically and statically measured, the latter involves having the individual in a stationary standing position, from which results researchers have proposed impaired postural stability as a risk factor for falling.^{6,7} However, evidence regarding the association of postural instability with prospective falls is limited, and population-based cohort studies in this field are scarce.⁸ Other shortcomings of previous studies include the use of retrospective study designs,⁹ which increase the risks of recall bias and the identification of risk factors as the result of falls.^{10,11}

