Postural instability is preferably investigated using objective measures of posturography, the advantages of which over regular clinical assessments include the reduction of test performance variability and avoidance of subjective scoring systems.¹² Recently, researchers have analyzed the performance of the Wii Balance Board (WBB; Nintendo, Kyoto, Japan) in the measurement of postural instability; WBB-based assessment has shown excellent concurrent validity and the ability to complement existing fall assessments.^{13,14}

As of 2012, all 70-year olds in the Umeå municipality are invited to participate in the Healthy Ageing Initiative (HAI) study, which has currently enrolled more than 3000 participants.

Among other measurements, we include assessment of postural stability using a Wii Balance Board (WBB; Nintendo, Kyoto, Japan) device. With each participant in a quiet stance, balance trials consisting of 60-second eyes-open (EO) and eyes-closed (EC) trials are performed. Participants are instructed to maintain an upright position throughout the test, stand relaxed, and avoid any arm or head movement. The WBB measures total COP sway length, representing the sum of postural sway in the anteroposterior and mediolateral directions.

Preliminary results from our analysis of data consisting of 1900 70-year-old individuals revealed that participants with postural sway in the 5th quintile had almost twice the risk of

falling compared to the reference group, when the 1-year follow-up of prospective falls was performed.

Thus the aim of the present follow-up study is to investigate if we can reduce the increased postural sway of participants who have been identified as having abnormal balance values, based on previous measurements.

Project description

Study design

The present project is planned to be conducted as a 4-week randomized intervention study with a follow up time of 2 years.

Study population

Recruitment of individuals at high risk of falls from the Healthy Ageing Initiative

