The Healthy Ageing Initiative (HAI) is an ongoing population based project aiming to reduce risk factors for non-communicable diseases (NCD) by risk factor evaluation and increased physical activity.¹⁵ In short, HAI is inviting all 70 year olds in Umeå municipality to a health examination where traditional and potential novel risk factors for diabetes, CVD and fractures are investigated. These include objective measures of physical activity, blood pressure, blood-glucose, objective measured abdominal fat mass and ectopic fat, bone density and other features of bone quality, cognitive function, balance, walking ability, and different life style factors. At the second visit, all participants are informed about the results of tests performed and gets advice with a focus on physical activity, aiming at decreasing the risk of future diabetes, CVD and fractures. The counseling with focus on physical activity is based on motivational interviewing (MI) which is a directive patient-centered counseling style to help the participants to explore and resolve their ambivalence about behavior change. They are

contacted at 6 months and 12 months per telephone for follow up and are contacted for an in-clinic follow up after 5 years.

Participants in HAI identified as being in the highest quartile of measures of postural sway, indicating poor balance and high fall risk, are invited to participate by telephone contact, and will upon agreement be randomized into either the intervention group or control group.

Participants will after the initial contact also receive written information about the study. We aim to recruit 90 individuals from the existing HAI study cohort

Study protocol

Please see figure 1 for figure of study protocol.

Intervention protocol

Group 1

Twenty participants are randomised into the intervention group. The intervention group will perform group training sessions a week, consisting of 30 minutes of training for 4 weeks.

Group 2

Forty participants are randomised into the control group and receive a health consultation that highlights the importance of physical activity and balance exercise according to standard practice within the HAI project. They are asked to return after 4 weeks for follow up.

Follow up

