Participants will also be asked to perform the Time-Up-and-Go (TUG) test,¹⁸ commonly used by clinicians to assess lower leg muscle strength, gait performance and overall functional mobility in elderly individuals. Testing involves participants rising unaided from an armchair and walking forward 3 meters until they reach a selected line on the floor, at which point they turn and come back to a seated position. Research nurses provides instructions and measures total testing time using a stopwatch. The TUG test have previously demonstrated good inter-

rater reliability (ICC=0.99).¹⁸ Testing of isometric muscle strength involves using a hydraulic hand dynamometer (Jamar, Patterson Medical, Warrenville, IL, USA) to measure participant's maximum grip strength in the non-dominant hand. Participants will be instructed to keep the arm angled at 90° and maintain the elbow in proximity to the waist during the test. The maximum value out of 2 consecutive attempts is subsequently recorded.

Measurement of Confidence in Balance Ability and Fear-of-Falling

Participants will also be asked to report confidence in balance ability and fear of falling. This will be accomplished through two questionnaires. The Falls Efficacy Scale International (FES-I) measures fear of falling and is comprised of 16 questions on a scale from 1-4.¹⁹ The Original Falls Efficacy Scale (FES) is also included and measures confidence in balance ability, formed by answering 13 questions on a scale from 1-10.²⁰

Anthropometric measures

Anthropometric data will be obtained using a scale (HL 120; Avery Berkel, Fairmont, MN, USA) to measure weight, and a gauge (Holtain Limited; Crymych, Dyfed, UK) to measure height.

Statistical analysis plan

Descriptive data will be presented as means + standard deviations and the Student's t-test will be used to analyze statistical differences between variables. Categorical variables are investigated using chi-squared tests. Potential differences between intervention and control group will be analyzed using paired and independent t-tests. All analyses will be performed with SPSS version 24 (IBM Corp, Armonk, NY, USA) and Stata version 13.1 (StataCorp, College Station, Texas, USA).

Ethical considerations

Importance

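### The SAP names no analysis for falls (aim 4), and its general t-test and chi-squared rules neither use follow-up time nor give a rate ratio

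*Combined protocol and SAP*

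**What the plan says.** Under Specific aims, the last aim (printed with two numbers, 4 and 3) asks whether balance training "leads to reduced number of falls at follow-up after 6, 12 and 24 months". Study design describes a "4-week randomized intervention study with a follow up time of 2 years". The Follow up section describes falls contacts at 6 and 12 months only. It does not state the date from which those months run.

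The Statistical analysis plan is one short paragraph. After means and standard deviations it says that the Student's "t-test will be used to analyze statistical differences between variables. Categorical variables are investigated using chi-squared tests". For the arms it says: "Potential differences between intervention and control group will be analyzed using paired and independent t-tests". It names no falls endpoint, rate, person-time, effect measure for falls, or rule for participants whose falls follow-up is incomplete. No other section supplies one.

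On numbers, Study population says "We aim to recruit 90 individuals from the existing HAI study cohort", while Intervention protocol says "Twenty participants are randomised into the intervention group" and "Forty participants are randomised into the control group". These arms sum to 60, not 90.

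**The concern.** A number of falls is a count that accumulates over time, and over a follow-up of up to two years some participants will probably be observed for less than the full period. If the SAP's general rules are applied, falls are analysed either as raw counts by an independent t-test or as faller/non-faller by chi-squared. A paired t-test does not compare the arms. The t-test has no term for time at risk. Chi-squared also has none, and it discards repeat falls.

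Two things are at stake. First, the result depends on an unstated choice about partial follow-up, which would be made after the data are seen. Second, a small comparison is most useful as a rate ratio with a confidence interval, which can be read and pooled. Neither planned test gives one.

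**Working it through.** The documents give no fall rate, dispersion, dropout, alpha or power figure, so there is no stated result to reproduce. Apart from the arm sizes and total, every input below is an assumption.

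**1. Bias when partial counts are used as full counts.** Let a proportion *d* of an arm leave, uniformly over the window. Mean observed time is (1 − *d*) + *d*/2 = 1 − *d*/2 of the window. With no true effect, the expected ratio of raw mean counts (training/control) equals the ratio of mean observed times.

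| Dropout, training / control | Calculation | Raw ratio |
|---|---|---|
| 10% / 20% | 0.95 / 0.90 | 1.06 |
| 10% / 30% | 0.95 / 0.85 | 1.12 |
| 10% / 40% | 0.95 / 0.80 | 1.19 |
| 30% / 10% | 0.85 / 0.95 | 0.89 |
| equal in both arms | – | 1.00 |

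Simulation agrees (1.11 to 1.12 for 10%/30%). Restricting to participants with complete contact gives 0.99 to 1.01 when dropout is unrelated to falls, but discards partial follow-up.

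Suppose instead that people prone to fall leave twice as often (10% vs 30% overall). The raw ratio is then 1.14 to 1.16, contacted-only 1.08 to 1.10, and the negative binomial model with offset 1.01 to 1.03. The offset reduces this bias but does not guarantee its removal.

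**2. Power at 20:40, full follow-up.** Assume negative binomial falls with control mean 0.3 (shape 0.5), or 0.5, 1 and 2 (shape 1), two-sided 5%, rate ratio 0.5. Simulated power:

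| Control mean | Pooled t | Chi-squared on fallers | Negative binomial likelihood ratio |
|---|---|---|---|
| 0.3 | 7% | 11% | 17% |
| 0.5 | 16% | 18% | 25% |
| 1 | 25% | 24% | 35% |
| 2 | 37% | 26% | 47% |

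Type I error of the likelihood-ratio test is about 5% to 6%.

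A closed-form check of the last column uses the variance of the log rate ratio, (1/μ₁ + k)/n₁ + (1/μ₂ + k)/n₂, with k = 1/shape. For control mean 1 it is (1/0.5 + 1)/20 + (1/1 + 1)/40 = 0.15 + 0.05 = 0.20. Power is Φ(0.693/√0.20 − 1.96) = Φ(−0.41) = 34%. The four settings give 15/23/34/46%, close to the simulation.

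**3. Where the gain over pooled t comes from.** The count variance is μ + μ²/shape. At control mean 1 it is 0.75 in training and 2 in control.

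- True variance of the difference in means: 0.75/20 + 2/40 = 0.0875.
- Pooled-variance version: [(19 × 0.75 + 39 × 2)/58] × (1/20 + 1/40) = 1.59 × 0.075 = 0.119.
- The pooled standard error is too large by √(0.119/0.0875) = 1.17.

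With equal arms the two variances coincide. Accordingly, at 45:45 the simulated gain over pooled t is only about 2 to 4 points (22/36/52/69% vs 26/39/55/71%).

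A Welch t-test at 20:40 has power of 21/31/41/54%, so there is no gain over it. Under no effect, however, it favours training 3.8% to 5.1% of the time against a nominal 2.5%.

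**4. Smaller effects.** At rate ratio 0.8 and 20:40, power is 4% to 7% for pooled t and 7% to 10% for the likelihood-ratio test.

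**5. Sparse data.** With 20 trained and rate ratio 0.5, the chance of no falls in that arm is 1.3⁻¹⁰ = 7.3% at control mean 0.3, and 1.25⁻²⁰ = 1.2% at 0.5.

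**The case against.** The strongest reply is that the SAP never assigns a test to falls, so criticising the t-test attacks something the plan does not say. That is fair. The documents support the narrower statement that no falls analysis is given and that only the general rules could apply.

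Aim 4 is also worded as a number of falls at fixed time points. Over a common, complete window a difference in mean counts answers that question, and type I error of the pooled t-test stays near nominal. This stands: preferring a rate ratio is good practice, not a requirement of the aim.

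A reader might infer that the planned falls comparison is biased. The documents do not support that. The bias needs dropout that is unequal or related to falls, and no dropout figure is given. When follow-up varies equally in both arms there is no bias, and the offset adds only 0 to 2 points of power. The dropout calculations also use uniform leaving times. With contacts at 6 and 12 months, observed time would move in steps, so those figures are illustrations.

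A reader might also infer a general loss of power. That depends on pooled variance at 20:40, and the total of 90 leaves the allocation unsettled. Pooled variance is the natural reading, because Student's is named in the first sentence, but the between-group sentence does not specify it.

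The rate ratio of 0.5 is optimistic. The Background reports that "participants with postural sway in the 5th quintile had almost twice the risk of" falling relative to its reference group. That is a risk rather than a fall rate, and enrolment is from the highest quartile rather than that quintile. Both groups are also offered the programme after the 4-week measurements, which would dilute a contrast.

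**Conclusion.** The point holds as a cheap improvement worth considering. The SAP gives no analysis for aim 4 and no rule for partial falls follow-up, and its general tests neither use time at risk nor yield a rate ratio. A concrete, better method is available.

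The size is modest and rests on assumed fall rates, dispersion and dropout. The power advantage is about 9 to 10 points over pooled t for a halving of falls at 20:40, and little or none under the other readings of the allocation and test. The protection against unequal follow-up matters only if such inequality occurs.

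It would be wrong to read this as showing that the planned test is invalid, or that the change would make aim 4 conclusive. Under these assumptions the comparison stays underpowered at 20:40. Falls is also the last-listed aim, while the title and first aim concern sway. The unanchored falls window affects both arms alike, so it is a gap in definition rather than a bias.

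**What to change.** Add to the Statistical analysis plan:

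> The number of falls from randomisation to 12 months, and to 24 months if falls are collected then, is compared between groups by negative binomial regression with log observed follow-up time as offset, reporting the rate ratio with 95% CI. The 6-month result is reported in the same way. The comparison is exploratory. Participants with incomplete follow-up contribute the time up to their last falls contact; their number and observed time are tabulated by group. If the model does not converge or a group has no falls, falls and person-years are reported by group.

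Record the randomisation date and the date of each falls contact. At each contact, ask about falls since randomisation or since the previous contact. Without this, the dates alone do not fix the counting window. Chi-squared on fallers can stay as a supportive analysis.

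Reconcile two sets of statements: the total of 90 with arms of 20 and 40, and the 24-month aim and two-year follow-up with falls contacts described only at 6 and 12 months.

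The cost is one SAP paragraph, a few dates per participant and consistent wording at the contacts. The downsides are slightly more analysis work, a slightly liberal test at these sizes, and possible non-convergence with few falls, which is why the fallback is included.

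### With the stated 20:40 split, the plan should name Welch's t-test for between-arm comparisons, because pooled intervals are mis-sized if training changes the spread (minor)

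*Combined protocol and SAP*

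**What the plan says.** All the relevant test wording is in the Statistical analysis plan. After the sentence on descriptive data it states that "the Student's t-test will be used to analyze statistical differences between variables". For the comparison of arms it adds: "Potential differences between intervention and control group will be analyzed using paired and independent t-tests". It does not mention Welch's test, unequal variances or a variance check. The named packages are SPSS 24 and Stata 13.1.

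The Intervention protocol gives the arm sizes: "Twenty participants are randomised into the intervention group" and "Forty participants are randomised into the control group". The section on the study population gives a different total: "We aim to recruit 90 individuals from the existing HAI study cohort". The plan states no significance level, standard deviation, effect size or power.

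**The concern.** The pooled test estimates one common variance, and the larger arm dominates that estimate. With equal arms this does little harm. With a 1:2 split, the standard error is too small when the smaller arm is the more variable, and too large when it is the less variable.

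Only one arm receives supervised training, so training could change the spread as well as the mean. The plan would then report intervals for sway, Timed Up and Go, FES-I and FES that do not have their nominal coverage. Which version of the test will be reported is also left open, although both named packages can produce either.

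**Working it through.** **Inputs.** From the documents: n1 = 20 (trained), n2 = 40 (control). Assumed, because the plan does not give them: two-sided 5% level, normal outcomes, and the ratio r of trained SD to control SD (control SD set to 1).

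**Stated sample size.** The target of 90 cannot be derived, since no inputs are given, and 20 + 40 = 60.

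**Formula.** In large samples the pooled test estimates the variance of the mean difference as

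V_pooled = [(n1·r² + n2)/(n1 + n2)] × (1/n1 + 1/n2),

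whereas the true variance is V_true = r²/n1 + 1/n2. The actual error rate is 2 × [1 − Φ(1.96 × √(V_pooled/V_true))], and interval coverage is one minus that.

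**Numbers at 20:40**, where 1/20 + 1/40 = 0.075:

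| r | V_pooled | V_true | 1.96 × √ratio | Error rate | Coverage |
|---|---|---|---|---|---|
| 0.8 | 0.880 × 0.075 = 0.0660 | 0.0320 + 0.025 = 0.0570 | 2.109 | 3.5% | 96.5% |
| 1 | 0.0750 | 0.0750 | 1.960 | 5.0% | 95.0% |
| 1.12 (r² = 1.25) | 1.0833 × 0.075 = 0.0813 | 0.0625 + 0.025 = 0.0875 | 1.889 | 5.9% | 94.1% |
| 1.25 | 1.1875 × 0.075 = 0.0891 | 0.0781 + 0.025 = 0.1031 | 1.821 | 6.9% | 93.1% |

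Simulation of the actual t-tests agrees with these rates to about 0.1 point. Over the wider range r = 0.5 to 2, the pooled rate runs from 1.7% to 11.2%; for r = 0.9 to 1.1 it is 4.3% to 5.8%. Welch's test (Satterthwaite degrees of freedom) stays between 4.9% and 5.0% throughout.

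**What could produce such ratios.** These are illustrations, not figures from the plan. If half the trained arm improves by d control SDs, independently of baseline, r = √(1 + 0.25d²): 1.12 for d = 1 and 1.25 for d = 1.5. If sway falls by 20% in proportion for everyone in the trained arm, r = 0.8.

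**Role of the split.** With n1 = n2 = n, V_pooled = (r² + 1)/n = V_true, so the large-sample distortion is zero. Simulated pooled rates for splits that sum to 90:

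| Split (trained:control) | r = 0.8 | r = 1.25 |
|---|---|---|
| 45:45 | 5.1% | 5.0% |
| 30:60 | 3.5% | 6.8% |
| 20:70 | 2.7% | 8.2% |
| 50:40 | 5.6% | 4.5% |

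**Cost of Welch's test at 20:40 with equal spreads.** At a difference of 0.8 SD, power is 81.9% pooled and 81.2% Welch. At the difference giving 80.0% pooled power (0.78 SD), Welch gives 79.2%. The loss is 0.4 to 0.8 points for differences of 0.5 to 1.0 SD.

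**Skewed outcome** (lognormal, σ = 0.6, 20:40, r = 0.5 to 2): pooled 2.5% to 11.5%, Welch 4.6% to 6.6%.

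**The case against.** The case for leaving the text alone has five parts.

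- **The plan never says pooled or equal variances.** Student's name appears in a general sentence; the sentence on arms says only independent t-tests. It is fair that the pooled version is an inference from standard usage. But if the wording is read as open, the version still has to be named.
- **The allocation is not settled.** This stands. The arm sizes and the target conflict, and equal arms would nearly remove the problem.
- **A reader might infer that false positives could reach 11%.** The documents do not support that. If training affects nobody, randomised arms have equal spread and the pooled test holds its level. In the half-respond scenario there is a true mean effect of 0.5 or 0.75 SD, so rejection is not a false positive, and pooled rejection in the wrong direction was simulated at 0.02% or less. The cost there is interval coverage of about 94% or 93%. By the same formula, ratios of 1.5 and 2 need half the arm to improve by √5 = 2.24 or √12 = 3.46 SDs.
- **A reader might infer that the trained arm will be the more variable one.** The documents do not support that either. Participants come from the highest quartile of sway; if the worst improve most, or improvement is proportional, the trained arm becomes less variable and the pooled test is conservative.
- **Larger gaps come first.** This stands. The missing significance level, primary outcome and sample-size basis matter more.

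None of these favours keeping the pooled test at 20:40, because Welch's test holds its level in both directions and costs little when the spreads are equal.

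**Conclusion.** The point holds as a minor one. At the stated 20:40 split, the pooled t-test gives mis-sized intervals and p-values if training changes the spread. For moderate changes (SD ratio 0.8 to 1.25), coverage is about 96.5% down to 93% against a nominal 95%; Welch's test stays near 95%.

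This rests on an assumed two-sided 5% level, roughly normal outcomes, assumed SD ratios, the standard reading of Student's t-test, and the arm sizes as written. The direction is unknown. The paired within-arm tests are not affected.

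**What to change.** Add one sentence to the Statistical analysis plan: between-arm comparisons of continuous outcomes use Welch's unequal-variance t-test (in SPSS, the line with equal variances not assumed; in Stata, the unequal option), without a preliminary test of variances. Reconcile the arm sizes of 20 and 40 with the target of 90, and state the allocation ratio.

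The cost is one sentence, no new software, and under one percentage point of power if the spreads are equal. With a strongly skewed outcome, Welch's test reduces the error but does not fully remove it (up to 6.6% in the skewed example, against 11.5% pooled).
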